4.2 Study Endpoints

4.2.1 Primary

1. To determine the safety and tolerability of SNS-301 delivered by intradermal injection (ID) using the 3M® hollow microstructured transdermal system (hMTS) device in addition to pembrolizumab among patients with locally advanced unresectable or metastatic/recurrent SCCHN as measured by the following parameters:
 - All adverse events (AEs) by CTCAE v5 such as clinically significant changes in safety laboratory parameters from baseline: CBC with Differential; Chemistry Panel; Urinalysis; T3, Free T4 and TSH; creatine phosphokinase (CPK) and including adverse events of special interest (AESI) classified by system organ class (SOC), preferred term (PT), severity and relationship to drug
2. To determine anti-tumor activity of SNS-301 delivered by intradermal injection (ID) using the 3M® hollow microstructured transdermal system (hMTS) device in addition to pembrolizumab in patients with locally advanced unresectable or metastatic/recurrent SCCHN as measured by the following parameters:
 - Objective response rate (ORR) by immune Response Evaluation Criteria in Solid Tumors (iRECIST)Duration of Response (DoR) as assessed by RECIST version 1.1 and iRECIST
 - Objective response rate (ORR) by Response Evaluation Criteria (RECIST) version 1.1 by investigator review
 - Disease control rate (DCR) as assessed by RECIST version 1.1 and iRECIST
 - Progression Free Survival (PFS) as assessed by RECIST version 1.1 and iRECIST
 - Overall Survival (OS)

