9.2.6 *Clinical Safety Laboratory Assessments*

Hematological toxicities will be assessed in term of hemoglobin value, white blood cell, neutrophil, platelet and, lymphocyte count according to NCI-CTCAE V5.0 AE grading.

Laboratory abnormalities (grade 1 and greater that are listed in the NCI-CTCAE V5.0) should be recorded on the AE page regardless of their causality. Laboratory abnormalities associated with a definitive diagnosis will not be recorded as an AE unless it has become worse since baseline. Test analytes are provided in the table below.

See the Time and Events Schedule for timing and frequency. Safety labs will be performed within 72 hours of each dosing visit.

Hematology	Serum chemistry
Hematocrit (Hct)	Albumin
Hemoglobin (Hgb)	Alanine aminotransferase (ALT)
Platelet count	Aspartate aminotransferase (AST)
Red blood cell (RBC) count	Alkaline phosphatase (ALP)
White blood cell (WBC) count	Blood Urea Nitrogen (BUN) or Urea
Neutrophils	Bicarbonate or Carbon dioxide (CO ₂)
Lymphocytes	Creatinine
Eosinophils	Creatine phosphokinase (CPK)
Monocytes	Electrolytes (Na, K, Mg, Cl, Ca, P)
Basophils	Glucose (either fasting or non-fasting)
Other cells, if any	Lactate dehydrogenase (LDH)
Thyroid	Total bilirubin (direct bilirubin if elevated)
TSH, T3 and FT4	Total protein
Coagulation	Urinalysis
International normalized ratio/INR	Specific gravity
Activated partial thromboplastin time (PTT)	pH
Other anticoagulant monitoring (if required)	Glucose
HIV screen (at screening, if indicated)	Protein
Hepatitis screen (at screening, if indicated)	Ketones
HPV/EBV screen (at screening, if unknown)	Blood
Pregnancy test	Microscopic exam, if abnormalities

9.2.7 *Hepatitis and HIV Screening*

Patients should be tested for HIV locally prior to the inclusion into the trial only based on investigator's clinical suspicion for HIV infection and HIV-positive patients will be excluded from the clinical trial. Hepatitis B surface antigen, anti-HBc antibody, anti-HBs antibody, and Hepatitis C antibody immunoassays should be tested only per investigator's clinical suspicion during screening and tested locally. In patients who have positive serology for the anti-HBc antibody, HBV DNA should be tested prior to Day 0.

9.2.8 *Pregnancy Test*

A Serum pregnancy test (for women of childbearing potential, including women who have had a tubal ligation) must be performed and documented as negative within 72 hours prior to each dose.

9.2.9 *Urinalysis*

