9.3 Adverse Events and Serious Adverse Events

9.3.1 *Definition of Adverse Event (AE)*

Adverse event is defined as any untoward medical occurrence associated with the use of a drug in humans, whether or not considered drug related. Any AE that occurs prior to the first dose is part of the medical history. AEs will be collected from the time of informed consent until 30 days after the last dose of study treatment or until initiation of another anti-cancer therapy, whichever occurs first.

Abnormal laboratory values should not be listed as separate AEs if they are considered to be part of the clinical syndrome that is being reported as an AE unless worsened on study treatment. It is the responsibility of the Investigator to review all laboratory findings in all patients and determine if they constitute an AE. Medical and scientific judgment should be exercised in deciding whether an isolated laboratory abnormality should be classified as an AE. Any laboratory abnormality (grade 1 and greater that are listed in the NCI-CTCAE V5.0) considered to constitute an AE should be reported on the Adverse Event CRF.

Pre-planned procedures (surgeries or therapies) that were scheduled prior to the start of study drug exposure are not considered AEs. However, if a pre-planned procedure is performed earlier than anticipated (e.g., as an emergency) due to a worsening of the pre-existing condition, the worsening of the condition should be captured as an AE.

Progression of the cancer under trial is not considered an adverse event unless it is considered to be drug related by the investigator. Patients will be encouraged to spontaneously report any AE. Patients will be questioned and/or examined by the Investigator and his/her medically qualified designee for evidence of AEs. The questioning of study patients with regard to the possible occurrence of AEs will be generalized, such as, "How have you been feeling since your last visit?" Information gathering for AEs should generally not begin with direct solicitation from patients regarding the presence or absence of specific AEs. Study personnel will ask open-ended questions to obtain information about AEs at every visit. Date and time of onset and resolution (if applicable) of the AE will be documented in the patient's clinical notes.

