Safety evaluations will be based on the incidence, severity, attribution and type of AEs, and changes in the patient's vital signs, and clinical laboratory results, analyzed using the safety analysis set.

Summarization of toxicity data will focus on incidence of treatment-emergent adverse events. Treatment-emergent adverse events are defined as any AE that occurs during or after administration of the first dose of treatment through 30 days after the last dose, any event that is considered study drug-related regardless of the start date of the event, or any event that is present at baseline but worsens in intensity. The incidence of serious adverse events, adverse events, drug-related adverse events, and adverse events leading to discontinuation or death will be presented in tabular form by system organ class and preferred term. Adverse events will be assessed for severity according to the NCI CTCAE, version 5.0.

A presentation of dose-limiting toxicities among patients in the safety run-in set will be presented.

Other safety evaluations including vital sign, laboratory and physical exam results will be presented over time.

10.4.4 *Other Analyses*

Antigen-specific cellular immune response assessed by but not limited to Interferon- γ secreting T lymphocytes will be summarized by visit. Immune related gene expression will be evaluated with pre- and post-treatment tissue biopsies. Cytokine and chemokine profiles will be summarized by visit.

Additional exploratory analyses may be performed, including evaluation of relationship between efficacy endpoints and immunology parameters.

10.4.4.1 *Pharmacodynamics*

Exploratory pharmacodynamic (PD) analysis will be performed using dose, vaccine-specific antibody response (geometric mean titer), antigen-specific T and B cell indices, and the relative expression of ASPH in each patient's tumor. The PD will be balanced and optimized to the degree of antigen-specific immune response and minimized for the production of regulatory immune processes.

10.5 *Interim Analyses*

For each cohort, the objective response rate will be assessed at the completion of stage 1 of the 2-stage design, after 15 patients complete the 12-week follow-up period or discontinue prior due to disease progression. See Section 10.2 for additional details.

10.5.1 *Safety Committee*

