#### 8.4 Clinical Safety Laboratory Assessments

Hematology, serum chemistry, coagulation and urinalysis data will be collected as specified in the study schedule of Assessments (Appendix A). Hematological toxicities will be assessed according to NCI-CTCAE V5.0 AE grading.

All laboratory results will be presented in the listings. Abnormal laboratory values with their clinical significance status will be presented in a listing. The laboratory tests cut off values are presented in Appendix B.

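### Protocol 9.2.6 and 9.3.1 give different rules for recording an isolated low-grade laboratory abnormality as an adverse event, so the laboratory part of TEAE incidence depends on which section a site follows

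*Protocol*

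**What the plan says.** Protocol 9.2.6 (Clinical Safety Laboratory Assessments) gives a recording instruction with no judgement step: "Laboratory abnormalities (grade 1 and greater that are listed in the NCI-CTCAE V5.0) should be recorded on the AE page regardless of their causality". The next sentence supplies its one exception: "Laboratory abnormalities associated with a definitive diagnosis will not be recorded as an AE unless it has become worse since baseline".

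Protocol 9.3.1 (Definition of Adverse Event) puts the decision with the investigator: "It is the responsibility of the Investigator to review all laboratory findings in all patients and determine if they constitute an AE". For isolated values it adds: "Medical and scientific judgment should be exercised in deciding whether an isolated laboratory abnormality should be classified as an AE". It then repeats the Grade 1 threshold of 9.2.6 with a condition attached: the abnormality must be one "considered to constitute an AE should be reported on the Adverse Event CRF". Its own exception covers values that belong to a clinical syndrome already reported as an AE, unless they worsen on study treatment.

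The primary safety endpoint in Protocol 4.2.1 is "All adverse events (AEs) by CTCAE v5 such as clinically significant changes in safety laboratory parameters from baseline". For the analysis, Protocol 10.4.3 says: "Summarization of toxicity data will focus on incidence of treatment-emergent adverse events".

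SAP 8.3 repeats the general AE definition. It tabulates any AE, any TEAE, treatment-related AEs, and TEAEs by system organ class, preferred term and maximum severity. It does not say when a laboratory value becomes an AE. On the laboratory data themselves, SAP 8.4 says: "Abnormal laboratory values with their clinical significance status will be presented in a listing". It also plans descriptive statistics, change from baseline, and shifts between low, normal and high.

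**The concern.** Take a single Grade 1 laboratory value with no accompanying diagnosis or syndrome. A site working from 9.2.6 enters it as an AE. A site working from 9.3.1 may decide that it is not an AE and enter nothing. Both sites have followed the protocol.

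Safety laboratory tests accompany each dosing visit (9.2.6) and up to 15 sites are planned (5.2), so there are many occasions for practice to diverge. AEs are a primary endpoint and TEAE incidence is the main safety summary. At stake is whether the laboratory entries in those tables measure toxicity or a mixture of toxicity and local recording habit. The low-grade rows are the most exposed.

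**Working it through.** **Step 1. The two rules side by side, for one isolated Grade 1 value that is new since baseline.**

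- Under 9.2.6 the value is CTCAE-listed and Grade 1 or above, and the definitive-diagnosis exception does not apply. It is recorded.
- Under 9.3.1 it is not part of a reported syndrome, so judgement applies. It is recorded only if the investigator considers it an AE.
- The exceptions also differ. One turns on a definitive diagnosis and change since baseline; the other turns on a reported syndrome and worsening on study treatment.
- Neither document says which section governs.

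**Step 2. The plan's own AE figures.** Protocol 10.2 gives about a 95% chance of seeing at least one event for an AE of 18% incidence in 15 patients, and for one of 5% incidence in 60 patients. With P(at least one) = 1 − (1 − p)^n:

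- 1 − 0.82^15 = 94.9%
- 1 − 0.95^60 = 95.4%

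Both reproduce. They are correct for whatever incidence is actually recorded.

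**Step 3. Illustration only.** Let p be the true patient incidence of an isolated abnormality and s the share that investigators judge to be AEs. The documents give no value of s, so 10% to 100% is an assumed range. Recorded incidence is s × p, and P(at least one recorded) = 1 − (1 − s × p)^n. Full recording under 9.2.6 corresponds to s = 100%.

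| s | Recorded incidence, p = 18% | P(at least one), n = 15 | Recorded incidence, p = 5% | P(at least one), n = 60 |
|---|---|---|---|---|
| 100% | 18% | 94.9% | 5% | 95.4% |
| 50% | 9% | 75.7% | 2.5% | 78.1% |
| 25% | 4.5% | 49.9% | 1.25% | 53.0% |
| 10% | 1.8% | 23.8% | 0.5% | 26.0% |

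Recorded incidence scales directly with s. If sites divide between the two rules, the result lies between the top row and the row for the s in use. The table shows the mechanism and does not estimate the effect in this trial.

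**Step 4. What the rule does not touch.** The laboratory DLT criterion in 9.3.8 sets its own Grade 3 and 4 conditions. Sample size, power and alpha in 10.2 rest on objective response.

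**The case against.** The best defence is that the two sections can be read together. On that reading, 9.2.6 only says that attribution must not filter what is recorded, while 9.3.1, as the definition of an AE, supplies the classification step. This is possible, but the text does not say it. The second sentence quoted from 9.2.6 lists what is not to be recorded as an AE, so that section is itself setting the AE rule, with one exception, and investigator judgement is not that exception.

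Three further points stand and narrow the issue:

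- **Overlapping exceptions.** Both sections leave out some values tied to a wider diagnosis or syndrome, so the dispute is essentially over isolated abnormalities. A reader might infer that 9.2.6 makes every Grade 1 or higher value an AE; its exception rules that out.
- **The TEAE definition.** Under 10.4.3 an abnormality present before dosing counts only if it worsens or is considered drug-related. Eligibility admits some abnormal baselines (for example AST/ALT up to 2.5 × ULN), so many stable values would not become TEAEs under either rule.
- **Separate laboratory reporting.** The SAP lists all results and tabulates change and shifts, so a laboratory signal would not vanish. The cover is partial: shifts are low/normal/high, and no summary table by CTCAE grade is planned.

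**Conclusion.** The inconsistency is real and unresolved. It affects the laboratory part of TEAE incidence, mainly low-grade events. Its size cannot be calculated from the documents; the table above rests on assumed shares. It is worth correcting because it feeds a primary safety output, but it does not threaten the design.

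Four stronger readings are tempting, and the documents do not support them.

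- **A third recording rule in 4.2.1.** The mention of clinical significance there is introduced as an example within an endpoint that covers all AEs. It adds some ambiguity but sets no threshold for recording.
- **A large computed effect.** Assuming an abnormality at 20–50% of visits gives 1 − 0.8^4 = 59% to 1 − 0.5^4 = 94% of patients by the fourth visit. That rate has no source. The Day 0 sample is taken before dosing, and three samples give 49–88% (1 − 0.8^3 to 1 − 0.5^3). Visits are also treated as independent; with full persistence within a patient the figure stays at 20–50%.
- **The 82% (9/11) TEAE rate in 3.1.2 cannot be interpreted.** If 9.3.1 had been followed, a switch to 9.2.6 could raise it to 11/11 at most. In the other direction, the documents do not say how many of the nine patients had only laboratory events. Section 3.1.2 also gives severity, relatedness and the Grade 3 terms, so this is a caveat on the figure.
- **A biased comparison between cohorts.** No such comparison is planned. Both cohorts use the same text and are summarised descriptively, so no differential effect is shown.

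**What to change.** 1. **Protocol 9.2.6 and 9.3.1:** reconcile them into one recording rule, worded identically in both places, with one common exception for abnormalities tied to a diagnosis or reported syndrome and one common reference point for worsening.
2. **SAP 8.3:** state that rule, so that the reader of the AE tables knows what a laboratory AE is.
3. **SAP 8.4:** add a summary of laboratory toxicity by worst CTCAE grade and by grade shift from baseline, derived from the laboratory data already collected. Laboratory toxicity rates then no longer depend on AE-page practice.

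The choice of rule belongs to the sponsor and is a trade-off. A judgement or clinical-significance threshold reduces low-grade entries, but abnormalities kept off the AE page lose their relatedness assessment, which the laboratory summaries do not carry. Recording all Grade 1 or higher values keeps that assessment at the price of more entries.

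The cost is a short site memo, one extra table, and possibly a review of laboratory AEs already entered. At the October 2020 cutoff, 11 of about 60 planned patients had been enrolled.

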9.2.14.3.1 Withdrawal from Future Biomedical Research

Patients may withdraw their consent for Future Biomedical Research and have their samples destroyed. Patients may withdraw consent at any time by contacting the principal investigator in writing. In turn, the Investigator will contact the Sponsor in writing. Subsequently, the patient's samples will be removed from the biorepository and be destroyed. No future data will be collected, but any data already collected from analysis of samples will remain with the Sponsor. A letter will be sent from the Sponsor to the investigator confirming the destruction. It is the responsibility of the investigator to inform the patient of completion of destruction. Any analyses in progress at the time of request for destruction or already performed prior to the request being received by the Sponsor will continue to be used as part of the overall research trial data and results. No new analyses would be generated after the request is received.

In the event that the medical records for the trial are no longer available (e.g., if the investigator is no longer required by regulatory authorities to retain the main trial records) or the samples have been completely anonymized, there will no longer be a link between the patient's personal information and their samples. In this situation, the request for sample destruction cannot be processed.

request for sample destruction cannot be processed.

9.2.14.4 Concomitant Medications

Concomitant medications include any prescription medications or over-the-counter medications. At screening, any medications the patient has used within the 7 days prior to the screening visit should be documented. At subsequent visits, changes to current medications or medications used since the last documentation of medications will be recorded. See Section [Prohibited Medications or Treatments During Study](#) for a list of prohibited medications.

Patients who are receiving anticoagulants will have anticoagulant specific drug level and/or anticoagulant specific factor X α levels obtained at baseline, at each administration of SNS-301, and at the end of study visit to ensure that these levels remain within therapeutic range throughout the duration of the trial. In the event of clinically noted bleeding, these tests will be obtained at the time of bleeding as well. Investigators should use tests routinely used in clinical practice to monitor patients receiving Warfarin, Heparin and/or Low Molecular Weight Heparins, along with the monitoring schedule provided above. Should there be two individual events of SNS-301 interruption for the same patients, then SNS-301 will be discontinued after consultation with the Medical Monitor and Study Sponsor. Clinical management and further workup of the coagulation pathway disturbance will be at the discretion of the investigator.

9.2.14.5 Adverse Events

AEs will be collected from the time of informed consent until 30 days after the last dose of study treatment or until initiation of another anti-cancer therapy, whichever occurs first. SAEs and AESIs will be collected from the time of informed consent until 90 days after the last dose of study treatment or until initiation of anti-cancer therapy, whichever occurs first. See Section 9.3 for additional details on Adverse Events and Serious Adverse Events.

9.2.14.6 Follow-Up

Survival follow-up information will be collected via telephone calls, patient medical records, and/or clinical visits approximately every 3 months for up to 3 years, until death, lost to follow-up, withdrawal of consent, or trial termination by Sponsor. All patients will be followed for survival and new anticancer therapy information unless the patient requests to be withdrawn from follow-up; this request must be documented in the source documents

and signed by the investigator. If the patient discontinues study treatment without documented clinical disease progression, every effort should be made to follow up regarding survival, progression (if not already progressed), and new anti-cancer therapy.

9.3 Adverse Events and Serious Adverse Events

9.3.1 *Definition of Adverse Event (AE)*

Adverse event is defined as any untoward medical occurrence associated with the use of a drug in humans, whether or not considered drug related. Any AE that occurs prior to the first dose is part of the medical history. AEs will be collected from the time of informed consent until 30 days after the last dose of study treatment or until initiation of another anti-cancer therapy, whichever occurs first.

Abnormal laboratory values should not be listed as separate AEs if they are considered to be part of the clinical syndrome that is being reported as an AE unless worsened on study treatment. It is the responsibility of the Investigator to review all laboratory findings in all patients and determine if they constitute an AE. Medical and scientific judgment should be exercised in deciding whether an isolated laboratory abnormality should be classified as an AE. Any laboratory abnormality (grade 1 and greater that are listed in the NCI-CTCAE V5.0) considered to constitute an AE should be reported on the Adverse Event CRF.

Pre-planned procedures (surgeries or therapies) that were scheduled prior to the start of study drug exposure are not considered AEs. However, if a pre-planned procedure is performed earlier than anticipated (e.g., as an emergency) due to a worsening of the pre-existing condition, the worsening of the condition should be captured as an AE.

Progression of the cancer under trial is not considered an adverse event unless it is considered to be drug related by the investigator. Patients will be encouraged to spontaneously report any AE. Patients will be questioned and/or examined by the Investigator and his/her medically qualified designee for evidence of AEs. The questioning of study patients with regard to the possible occurrence of AEs will be generalized, such as, "How have you been feeling since your last visit?" Information gathering for AEs should generally not begin with direct solicitation from patients regarding the presence or absence of specific AEs. Study personnel will ask open-ended questions to obtain information about AEs at every visit. Date and time of onset and resolution (if applicable) of the AE will be documented in the patient's clinical notes.

A suspected adverse reaction means any AE for which there is a "reasonable possibility" that the drug caused the AE. For the purpose of reporting under this protocol, "reasonable possibility" means there is evidence to suggest a causal relationship between the drug and the AE.

An AE is considered unexpected if the AE is not listed in the current IB or is not listed in the IB at the specificity or severity observed.

9.3.2 *Definition of Serious Adverse Event (SAE)*

A serious adverse event (SAE) is an AE that:

- Is fatal
- Is life-threatening, meaning the patient was, in the view of the Investigator, at immediate risk of death from the reaction as it occurred, i.e., it does not include a reaction that, had it occurred in a more serious form or progressed, might have caused death
- Is a persistent or significant disability or incapacity or substantial disruption of the ability to conduct normal life functions

- Requires or prolongs inpatient hospitalization
- Is a congenital anomaly or birth defect
- Other important medical events may be considered SAEs when, based upon appropriate medical judgment, they may jeopardize the patient and may require medical or surgical intervention to prevent one of the outcomes as listed above in this definition. Examples of such medical events include allergic bronchospasm requiring intensive treatment in an emergency room or at home, blood dyscrasias or convulsions that do not result in inpatient hospitalization, or the development of drug dependency or drug abuse

The Medical Monitor will advise the Investigator regarding the nature of any further information or documentation that is required. The Investigator should provide the following documentation at the time of notification if available:

- SAE Form
- AE (CRF) page
- Concomitant and support medication pages
- Relevant diagnostic reports
- Relevant laboratory reports
- Admission notes and hospital discharge summary (when available).

Clarification of Serious Adverse Events (SAEs)

- Death in itself is not an AE. Death is an outcome of an AE.
- Progression of the cancer under trial is not considered an adverse event unless it is considered to be drug related by the investigator.
- The patient may not have been receiving an investigational medicinal product at the occurrence of the event.
- Dosing may have been given as treatment cycles or interrupted temporarily before the onset of the SAE but may have contributed to the event.
- Complications that occur during hospitalizations are AEs. If a complication prolongs the hospitalization, it is an SAE.
- Inpatient hospitalization means that the patient has been formally admitted to a hospital for medical reasons, for any length of time. This may or may not be overnight. It does not include presentation and care within an emergency department nor does it include full day or overnight stays in observation status.

The following hospitalization scenarios are not considered to meet the criteria for a serious adverse events:

- Hospitalization for respite care
- Hospitalization to perform an efficacy measurement for the trial

- Hospitalization for an elective surgery for a pre-existing condition.

The Investigator will attempt to establish a diagnosis of the event on the basis of signs, symptoms, and/or other clinical information. In such cases, the diagnosis will be documented as the AE and/or SAE and not the individual signs/symptoms.

9.3.3 *Classification of an Adverse Event*

9.3.3.1 *Severity of Event*

Adverse events will be graded by the Investigator using the NCI-CTCAE 5.0 graded 1-5. Grade refers to the severity of the AE. For events not described in the NCI CTCAE, the Investigator will assign grades as 1= mild, 2=moderate, 3=severe, 4=life-threatening, and 5=fatal based on this general guideline:

Grade 1: Mild; asymptomatic or mild symptoms; clinical or diagnostic observations only; intervention not indicated.

Grade 2: Moderate; minimal, local or noninvasive intervention indicated; limiting age-appropriate instrumental ADL*

Grade 3: Severe or medically significant but not immediately life-threatening; hospitalization or prolongation of hospitalization indicated; disabling; limiting self-care ADL**.

Grade 4: Life-threatening consequences; urgent intervention indicated.

Grade 5: Death related to AE. (Grade 5 (Death) may not appropriate for some AEs and therefore may not an option.)

The highest level of severity attained for each AE will be recorded in the CRFs.

Activities of Daily Living (ADL)

*Instrumental ADL refer to preparing meals, shopping for groceries or clothes, using the telephone, managing money, etc.

**Self-care ADL refer to bathing, dressing and undressing, feeding self, using the toilet, taking medications, and not bedridden.

